Serum calcium and phosphate blood samples will also be taken on Day 3 (±1 day), Day 5 (±1 day), Day 8 (±1 day), Day 11 (±1 day), Day 21 (±1 day), and Day 30. In addition, there may be additional and unscheduled checks for serum calcium and phosphate at the discretion of the Investigator. After the last study drug administration, if subjects are not entering the extension period, they will be instructed to resume their prestudy calcium and active vitamin D treatment regimen and doses based on assessments performed on Day 28/ET to Day 30.

Extension Phase

Extension phase will start immediately following Day 28 visit. On Days 29 onwards, patients will continue on the same dose of AZP-3601 as on Day 28, then individual titration of AZP-3601 may start as early as Day 30.

Patients will return to the clinical site for additional visits on Day 56 (±4 day), Day 84/ET (±4 day), and Day 85 (Day 84 + 1 day).

Serum calcium and phosphate blood samples will also be taken on Day 42 (±4 day), Day 70 (±4 day), and Day 86 (Day 84 + 2 days). In addition, there may be additional and unscheduled checks for serum calcium and phosphate at the discretion of the Investigator.

Patients will have their serum calcium/albumin levels measured within 5 days after any adjustment of AZP-3601 or any other time at the discretion of the investigator. The investigator will be free to perform any serum or urine test if needed.

After the last study drug administration, the patients will be instructed to resume their prestudy calcium and active vitamin D treatment regimen and doses based on assessments performed on Day 84 (\pm 4 day) to Day 86 (Day 84 + 2 days).

Follow-up

on Day 37 (±2 days). For patients entering the extension phase, follow-up visit will be on Day 98 (±4 days)

* For each study part, the planned treatment period, day of discharge, and follow-up period may be adapted depending on emerging study results.

Subjects/Patients

: Approximately 24 male or female subjects with HP who are on treatment with oral calcium and active vitamin D

Diagnosis and Main Criteria for Inclusion

	- within the normal range of the laboratory under standard of care
	If historical laboratory analysis (≥12 months) is not available, an additional
	recent concomitant laboratory measurement is required (with a minimum of
	3 weeks testing interval).
	- Requirement for therapy with calcitriol ≥0.25 µg per day or alphacalcidol
	≥0.50 µg per day (both are active vitamin D supplements), and requirement

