- b These visits are mandatory. As an alternative, these visits may be performed off-site; for instance, blood sampling may be performed at a local laboratory or at home by a study nurse. In addition, during the optimization period, there may be optional weekly visits.
- c A full physical examination will be done at screening, and on Day 28 (predose). An abbreviated physical examination will be done on Days 1, 14, and 16 (at predose), and 29, and at follow-up. Unscheduled symptom-directed physical examinations may be conducted at any time per the Investigator's discretion.
- d Single 12-lead ECG: at screening. The ECG will be recorded after the subject has been resting for at least 5 minutes in the supine position.
- e Supine systolic and diastolic blood pressure, pulse rate, and body temperature: at screening, on Day -1, on Days 1, 14, 15, and 28 at predose, on Day 29, and at follow-up. Vital signs will be recorded after the subject has been resting for at least 5 minutes in the supine position.
- f Subjects in Part C will receive AZP-3601 for 28 days as daily sc abdominal injections (with rotation of injection sites every dosing day). During the study visit the injection will be performed at the clinical site.
- g Blood sampling for ADA: on Day -1, on Day 28, and at follow-up. All samples will be analyzed. In case of positive ADA, patients will be monitored until the levels return to normal.
- h Injection site reaction: postdose on Day 1, predose and 1 hour postdose (when dosing) on Days 14, 15, 16, and 28, on Day 29, and at follow-up.
- i Blood sampling for PK of AZP-3601 in plasma: serial samplings on Days 1, 14, and 28 (predose, 5min, 10min, 20min, 30min, 1 hour and 2 hours post dose).
- j Serial sampling on Days 1, 14, and 28 (predose, 2 hours and 6 hours post dose). Samples will be taken fasting and pre-dose, except when profile where pre- and post-doses are taken
- k At any time during the study, hypercalcemia and hypocalcemia will be managed by adjustment in active vitamin D and/or oral calcium supplementation. Adjustments will be based on laboratory values including albumin-corrected serum calcium and serum phosphate as well as on symptoms and will be performed at the Investigator's judgment.
- Bone turnover biomarkers include serum bone-specific alkaline phosphatase, serum carboxy-terminal telopeptide of type I collagen, serum procollagen type 1 amino-terminal propeptide, and serum osteocalcin.

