- The schedule of assessment indicates the end of collection day of each 24h collection.Refer to Section 3.5.1.3.2 and Figure 4 for more details. m
- DXA scans can be obtained within 2 weeks prior to the Day 1 visit n
- 0
- Sample will be taken predose and fasting For patients willing to enter the extension phase, an ICF should be signed on Day 28 at the latest Only weight is measured at Day 28 Day 28: Dispense study drug to the patients participating to the extension phase p q
- r

Table 4 Schedule of Assessments - Part C Extension Phase

Assessment		Follow-up						
Day (Month)	D29-D30 ^p	42 ^b	56 (Month 1)	70 ^b	84/Early termination (Month 2)	85 (D84+1d)	86 ^ь D84+2d)	98
Visit Window (days)		±4	±4	±4	±4			±4
Informed Consent ^a								
Completion of Diary		Х	Х	Х	Х	Х	Х	Х
Physical Examination ^c			А		F	А		А
Body Weight					Х			
Serum Pregnancy Test (Females of childbearing potential Only)			Х		Х			
Clinical Laboratory (Clinical Chemistry, Hematology, Coagulation, and Urinalysis) (Fasted)			Х		x			Х
Vital Signs ^e			Х		Х	Х		Х
SARS-CoV-2 test ^m								
Study Drug Administration ^f		Х	Х	Х	Х			
Drug Accountability °			Х		Х			
Blood Sampling for ADA ^g			Х		Х			Х
Injection Site Reaction ^h			Х		Х	Х		Х
Blood Sampling for PK ^r					Х			
Blood Sampling: Total Calcium, Albumin Corrected Calcium, and Phosphate in Serum ⁱ		х	Х	х	х	x	х	Х
Active Vitamin D and Oral Calcium Supplementation Adjustment		х	Х	х	х	x	х	Х
Blood Sampling: Endogenous Serum PTH(1-84)			Х		Х			Х
Blood Sampling: Bone Turnover Biomarkers ^k			Х		Х			Х
Blood Sampling: 25Hydroxy Vitamin D (Native Vitamin D) and 1,25Dihydroxy Vitamin D in Serum			х		x			
Blood Sampling: Serum Magnesium			Х		Х			
Blood Sampling: Serum Creatinine ⁿ			Х		Х	Х		Х
24-Hour Urine Collection: Calcium, Phosphate, Creatinine (for Calculation of FECa of Calcium and Phosphate and for Calculation of TMP/GFR), and Magnesium ¹			x			x		Х
EQ-5D questionnaire					Х			
SF-36 questionnaire					Х			
DXA (bone mineral density) ^q					Х			
Previous and Concomitant Medication		X	Х	Х	Х	Х	Х	Х
AE Monitoring		X	Х	Х	Х	X	Х	Х

A=abbreviated physical examination; ADA=antidrug antibodies; AE=adverse event; ECG=electrocardiogram; F=full physical examination; FECa=fractional excretion; PD=pharmacodynamic(s); PK=pharmacokinetic(s); PTH=parathyroid hormone; sc=subcutaneous; SF-36=short form health survey 36; TMP/GFR=tubular maximum reabsorption of phosphate/glomerular filtration rate; DXA=dual-energy x-ray absorptiometry

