- a For patients willing to enter the extension phase, an ICF should be signed on Day 28 at the latest
- b These visits are mandatory. As an alternative, these visits may be performed off-site; for instance, blood sampling may be performed at a local laboratory or at home by a study nurse.
- c F=Full physical examination. A=Abbreviated examination. Physical Examination are done predose at visits when there is a dosing. Unscheduled symptom-directed physical examinations may be conducted at any time per the Investigator's discretion.
- d The 2 month open label treatment extension phase will start immediately following Day 28 visit of the Main treatment period. Patients will complete study assessments up to Day 28 as described in Table 3, and from Day 29 onwards as described in Table 4.
- e Supine systolic and diastolic blood pressure, pulse rate, and body temperature. Vital signs will be recorded after the subject has been resting for at least 5 minutes in the supine position. Vital Signs are done predose at visits when there is a dosing.
- f Subjects will receive AZP-3601 for 56 days (2 months), as daily sc abdominal injections (with rotation of injection sites every day of administration) from Day 29 onwards. On Day 29 onwards, patients will continue on the same dose of AZP-3601 as on Day 28 then individual titration may start as early as Day 30, and patients may have their dose of AZP-3601 adjusted at any time during the extension phase.

During study visits, the injection will be performed at the clinical site.

- g All blood sampling for ADA will be analyzed. In case of positive ADA, patients will be monitored until the levels return to normal.
- h Injection site reaction: predose and 1 hour postdose when there is a dosing
- i Serial sampling on Days 56 and 84 (predose, 2 hours and 6 hours postdose). Samples will be taken fasting and pre-dose, except when profile where pre- and post-doses are taken.
- j At any time during the study, hypercalcemia and hypocalcemia will be managed by adjustment in active vitamin D and/or oral calcium supplementation. Adjustments will be based on laboratory values including albumin-corrected serum calcium and serum phosphate as well as on symptoms and will be performed at the Investigator's judgment.
- k Bone turnover biomarkers include serum bone-specific alkaline phosphatase, serum carboxy-terminal telopeptide of type I collagen, serum procollagen type 1 amino-terminal propeptide, and serum osteocalcin.

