15.2.2.1 Dose-Proportionality

16.0 Pharmacodynamic and other Analysis

16.1 Pharmacodynamic and other Variables

16.1.1 Serum PD Concentrations and Parameters

Part C:

At the time points defined in the schedules of assessments, blood samples will be taken for the measurements of serum total calcium, serum albumin, albumin-corrected serum calcium, serum phosphate, serum creatinine (to calculate the fractional excretion (FECa) of calcium and phosphate), and endogenous serum PTH(1-84).

Serum PD variables include level/concentration of

- Serum total calcium
- Albumin-corrected serum calcium
 - Albumin-corrected serum calcium (mmol/L) = serum total calcium (mmol/L) + 0.020 (40 serum albumin [g/L])
- Serum phosphate
- Endogenous serum PTH(1-84).

Furthermore, serum AUC_{0-24} for albumin-corrected calcium is a serum PD variable, which is defined as area under the serum concentration-time curve from time zero up to 24 hours for albumin-corrected calcium.

EDSREP 009 T 01 G Page 25 of 53

Version Date: 26-Aug-2022

Part only:

In addition to the PD variables listed above, at the time points defined in the schedules of assessments, blood samples will be taken for the measurements of serum 25-hydroxy vitamin D, serum 1.25-dihydroxy vitamin D, serum magnesium and serum bone turnover biomarkers.

Serum PD variables include level/concentration of

- Serum 1.25-dihydroxy vitamin D
- Serum Magnesium
- Serum bone turnover biomarkers:
 - Serum bone-specific alkaline phosphatase (BSAP)
 - Serum carboxy-terminal telopeptide of type I collagen (s-CTx)
 - Serum procollagen type 1 amino-terminal propeptide (P1NP)
 - o Serum osteocalcin

Part C only:

In addition to the PD variables listed above, the following serum PD variables will be calculated:

- Serum calcium phosphate product
 - Serum calcium phospate product (mg2/dL2) = serum total calcium (mg/dL) * serum phosphate (mg/dL)
- Number of patients within the target range of albumin-corrected serum calcium
- Number of patients within the normal range of albumin-corrected serum calcium
- Number of patients within target range of albumin-corrected serum calcium who taking no vitamin D
 and taking <=500mg of oral calcium
- Number of patients within normal range of albumin-corrected serum calcium who taking no vitamin D and taking <=500mg of oral calcium,

where target range refers to 7.8 to 9.0 mg/dL and normal range refers to 8.3 to 10.6 mg/dL.

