16.1.2 Urine PD Concentrations and Parameters

Part C:

Urine will be collected during 24-hour collection intervals as defined in the schedules of assessments for the analysis of urine calcium, phosphate, creatinine (to calculate the FECa of calcium and phosphate and renal tubular maximum reabsorption of phosphate/glomerular filtration rate [TMP/GFR]),

and magnesium.

The urine PD variables include

- 24-hour urine calcium (calcium excretion rate) = concentration of urine calcium * volume 24h sample
- 24-hour urine calcium adjusted by creatinine = concentration of urine calcium in the 24h urine/
- 24-hour urine calcium adjusted by body weight ¹ = concentration of urine calcium * volume 24h sample / body weight
- 24-hour urine phosphate (phosphate excretion rate) = concentration of urine phosphate * volume 24h sample
- 24-hour urine cAMP (cAMP excretion rate) = concentration of urine cAMP * volume 24h sample

EDSREP 009 T 01 G Page 26 of 53

Version Date: 26-Aug-2022

- Renal clearance of calcium = Urine Ae₀₋₂₄ / Serum AUC₀₋₂₄ for albumin-corrected calcium, where Ae₀₋₂₄ is the total amount of calcium excreted unchanged into urine from time 0 to 24h
- Renal clearance of phosphate = Urine Ae₀₋₂₄ / Serum AUC₀₋₂₄ for phosphate, where Ae₀₋₂₄ is the total amount of phosphate excreted unchanged into urine from time 0 to 24h
- FECa of calcium $(\%)^2 = 100$ * urine calcium * serum creatinine / (serum calcium * urine creatinine)
- FECa of phosphate $(\%)^3$ = 100 * urine phosphate * serum creatinine / (serum phosphate * urine creatinine)
- Tubular reabsorption of phosphate (TRP) = 1 {(urine phosphate/serum phosphate) × (serum creatinine/urine creatinine)}
- Renal TMP/GFR = TRP × serum phosphate if TRP was ≤0.86; Renal TMP/GFR = 0.3 × TRP/[1 (0.8*TRP)] × serum phosphate
- 24-hour urine magnesium (magnesium excretion rate) = concentration of urine magnesium * volume 24h sample (Only for Part C)

Note 1: for 24-hour urine calcium adjusted by body weight: "body weight" refers to the last measurement of body weight before the start of 24-hour interval of urine collection for each day.

Note 2: for FECa of calcium (%): "serum calcium" refers to the measurement at start of 24-hour interval of urine collection for each day.

Note 3: for FECa of phosphate (%): "serum phosphate" refers to the measurement at start of 24-hour interval of urine collection for each day.

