16.2.1 Main PD Analysis

The main PD variables refer to the concentration of serum total calcium, albumin-corrected serum calcium and serum phosphate, as well as to the serum AUC_{0-24} for albumin-corrected calcium. The main PD variables will be summarized and listed in US standard units.

Descriptive statistics (n, arithmetic mean, SD, median, min, and max) summarizing the serum concentration for main PD variables (absolute observed value and change from baseline) will be presented by study part and ______/cohort (for Part C) at each scheduled timepoint/day. Taking potential batch effect into consideration, the change from baseline will be calculated with corresponding baseline per batch if applicable; for different batches, all the assessments (absolute observed value and change from baseline (when possible)) will be presented with corresponding batch information separately. For the daily pre-dose timepoints, if a repeat/retest result is available, then the repeat/retest (Batch R) result will be used for the calculations.

Descriptive statistics (n, arithmetic mean, SD, median, min, and max) will also be used to summarize the serum AUC_{0-24} for albumin-corrected calcium. Change from baseline for that AUC will be listed and summarized, which is defined as area under the serum concentration-time curve from time zero up to 24 hours for change from baseline of albumin-corrected calcium.

In Part A, linear plots of the arithmetic mean serum concentrations of main PD variables (absolute observed value and change from baseline) with SD over all scheduled timepoints will be presented by treatment. In Part B, similar linear plots (absolute observed value and change from baseline) will also be provided for each summary tables of serum concentration as described above and presenting only the 24h profile versus time on Day 1, Day 7 and Day 14 (separately). In part C, similar linear plots will be provided by cohort for the main treatment period and for the extension phase separately.

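### AUC0-24 of albumin-corrected calcium has no scheduled 24 h sample after Day 1 or Day 56, and AUC-based renal clearance has a matching serum profile only for urine collections ending on Days 29 and 85

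*SAP*

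**What the plan says.** SAP 16.1.1 lists, under Part C, a serum AUC0-24 "defined as area under the serum concentration-time curve from time zero up to 24 hours for albumin-corrected calcium". SAP 16.2.1 raises it to a main PD variable: the main variables are the calcium and phosphate concentrations "as well as to the serum AUC_{0-24} for albumin-corrected calcium". The same section adds a change version, taken "from time zero up to 24 hours for change from baseline of albumin-corrected calcium".

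Sampling is set in the protocol's schedules of assessments. Table 3, footnote j, for the main treatment period: "Serial sampling on Days 1, 14, and 28 (predose, 2 hours and 6 hours post dose". Table 4, footnote i, for the extension: "Serial sampling on Days 56 and 84 (predose, 2 hours and 6 hours postdose". After Day 1 the Study Schedule section gives the next samples: "Serum calcium and phosphate blood samples will also be taken on Day 3 (±1 day), Day 5 (±1 day), Day 8 (±1 day".

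SAP 16.1.2 defines renal clearance of calcium as Ae0-24 over the AUC0-24 of albumin-corrected calcium, where Ae0-24 "is the total amount of calcium excreted unchanged into urine from time 0 to 24h". Phosphate clearance uses a phosphate AUC0-24 in the same way. On urine timing, Table 3, footnote m, says: "The schedule of assessment indicates the end of collection day of each 24h collection"; Table 4 repeats this.

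**The concern.** An AUC over 24 h needs a sample at or near 24 h, or a stated rule in place of one. On Day 1 (first dose) and Day 56 (mid-extension) the Part C schedule supplies neither. For these days a main PD variable would be either missing or fixed by a choice made at analysis, possibly after the data have been seen.

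The clearance formula adds a second condition: numerator and denominator should cover the same 24 h. Because the urine days in the tables are end days, most collections precede the serum profile of the same date instead of running alongside it. Clearances computed by matching visit labels would pair urine from one day with serum from the next.

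**Working it through.** **Step 1. Does each profile reach 24 h?** Inputs: Protocol Tables 3 and 4 and the Study Schedule section.

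| Profile day | Times sampled | Next scheduled serum sample | Nominal hours after dose |
|---|---|---|---|
| 1 | 0, 2, 6 h | Day 3 ±1 | 48 (window 24 to 72) |
| 14 | 0, 2, 6 h | Day 15 | 24 |
| 28 | 0, 2, 6 h | Day 29 | 24 |
| 56 | 0, 2, 6 h | Day 70 ±4 | 336 |
| 84 | 0, 2, 6 h | Day 85 | 24 |

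On Days 1 and 56 the unobserved share is (24 − 6)/24 = 18/24 = 75%. After Day 56 the shortest gap the windows allow is (70 − 4) − (56 + 4) = 6 days. After Day 1, a patient has a 24 h value only if the Day 3 sample happens to be drawn on Day 2.

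**Step 2. Does the SAP fill the gap?** SAP 8.1.2 imputes nothing unless noted, and its exceptions do not include calcium or phosphate. SAP 8.1.5 keeps unscheduled samples out of the summaries, except for baseline. SAP 16.2.1 gives no interpolation or extrapolation rule for the calcium AUC. By contrast, SAP 7.1 drops the plasma drug AUC0-12 and AUC0-24, partly because of the sampling times; no such change is made for calcium.

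**Step 3. How much does the missing point matter?** The plan gives no figure to reproduce, so this is an illustration. Assumed calcium values are 8.4, 8.6 and 8.9 mg/dL at 0, 2 and 6 h, with baseline 8.4, the linear trapezoid, and a 24 h value c anywhere in the plan's target range of 7.8 to 9.0 mg/dL.

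- AUC0-6 = 2 × 8.5 + 4 × 8.75 = 52.0. Change-AUC0-6 = 2 × 0.1 + 4 × 0.35 = 1.6.
- Absolute tail = 18 × (8.9 + c)/2. For c = 7.8 this is 150.3, total 202.3. For c = 9.0 it is 161.1, total 213.1. Ratio: 213.1/202.3 = 1.053, about 5%.
- Change tail = 18 × [0.5 + (c − 8.4)]/2. For c = 7.8 this is −0.9, total 0.7. For c = 9.0 it is 9.9, total 11.5 mg·h/dL.
- The width, 18 × (9.0 − 7.8)/2 = 10.8 mg·h/dL, does not depend on the assumed 0, 2 and 6 h values or on the baseline.

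Two analyst choices for the same patient also differ. Reusing the predose value as the 24 h value gives 1.6 + 18 × (0.5 + 0)/2 = 6.1. Carrying the 6 h value forward gives 1.6 + 18 × 0.5 = 10.6.

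**Step 4. Which urine collections match a serum profile?**

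| Collection ends | Covers | Post-dose profile over the same 24 h? |
|---|---|---|
| Day 1 | 24 h before first dose | No; Day 1 profile follows it |
| Day 14 | Day 13 to 14 | No; Day 14 profile follows it |
| Day 29 | Day 28 to 29 | Yes |
| Day 37 (no extension) | Day 36 to 37 | No profile |
| Day 56 | Day 55 to 56 | No; Day 56 profile follows it |
| Day 85 | Day 84 to 85 | Yes |
| Day 98 (extension) | Day 97 to 98 | No profile |

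Days 37 and 98 are alternatives. A patient who stops at the main period has 4 scheduled collections, 1 of them matched; a patient who completes the extension has 6, 2 of them matched.

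**The case against.** The strongest reply is that the SAP never says AUC0-24 will be derived on Part C Days 1 or 56. The variable lists look shared with redacted study parts: urine cAMP is listed although neither Part C schedule collects it, and SAP 16.2.1 describes 24 h profiles for Part B. SAP Appendix 2, the table shells, and Protocol Section 3.5.1.3.2 with Figure 4 are not in the available text and might name the days. This stands as a limit on certainty. It does not remove the mismatch, since the readable SAP text lists the variable under Part C, and Protocol Tables 3 and 4 are explicit about sampling.

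Four stronger readings are tempting but unsupported:

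- A reader might infer that AUC0-24 cannot be derived in Part C at all. Days 14, 28 and 84 each have a next-day sample.
- A reader might infer that the software will extrapolate along a terminal slope. The SAP describes that only for plasma drug; for calcium the value could equally be left missing.
- A reader might infer that every drug effect on clearance is read against a baseline mixing untreated urine with treated serum. SAP 16.2.2.2 plans change from baseline for 24-hour urine calcium, phosphate and magnesium, not for clearance, and nowhere pairs the pre-dose collection with the Day 1 profile.
- A reader might carry the wide change-AUC range over to clearance. Clearance divides by the absolute AUC, which moves about 5% in the example.

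It is also fair that the secondary PD objective, maintenance within the target range, needs no AUC, that concentrations are summarised at every scheduled timepoint, and that no hypothesis is tested.

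**Conclusion.** The point holds in a limited form. On 2 of 5 Part C profile days (1 and 56), AUC0-24 of albumin-corrected calcium lacks 75% of its window and the SAP has no rule to supply it. The harm falls on the change-AUC: in the assumed example it runs from 0.7 to 11.5 mg·h/dL, while the absolute AUC stays between 202.3 and 213.1. For renal clearance the main defect is interval matching; only the collections ending on Days 29 and 85 fit the formula.

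This rests on the scheduled samples, on reading the urine table days as end days as the footnotes state, and on treating the Day 15, 29 and 85 samples as nominal 24 h points. The example's calcium values are assumed. The change is worth making because a named main variable and a stated formula are affected. It is not critical: the analysis is descriptive and the safety objective is untouched.

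**What to change.** Amend SAP 16.1.1, 16.1.2 and 16.2.1 for Part C:

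- Report AUC0-24 of albumin-corrected calcium, absolute and change, only for Days 14, 28 and 84, with the Day 15, 29 and 85 samples as the 24 h point and no extrapolation.
- Use AUC0-6, absolute and change, as the common profile summary on Days 1, 14, 28, 56 and 84.
- Compute AUC-based clearance of calcium, and of phosphate from its own AUC, only for the collections ending on Days 29 and 85.
- If a baseline clearance is wanted, base its denominator on the Day -1 and Day 1 predose serum values, which bracket that collection. Label it as a different kind of denominator from the on-treatment profile AUC.
- Rely on fractional excretion for comparison across visits. SAP 16.1.2 pairs it with serum at the start of each collection, but no serum sample is scheduled on Days 13, 36, 55 or 97. The SAP should therefore name the value used for the collections ending on Days 14, 37, 56 and 98.

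The cost is SAP wording and programming, with no added visits or samples. The downside is that AUC0-24 and clearance appear on fewer days. Even on Days 14, 28 and 84 nothing is sampled between 6 and 24 h, so those AUCs rest on one straight segment and should be footnoted accordingly.
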